8.3.3 Exploratory Endpoint(s)

Safety and tolerability will be measured by the incidence of all adverse events, serious adverse events, deaths and laboratory abnormalities. Adverse event assessments and laboratory tests will be performed at baseline, and continuously throughout the study at the beginning of each subsequent cycle.

Efficacy data will be assessed by measuring OS, DOR, ORR and PFS. These endpoints are defined as follows:

- OS is defined as the time from first dosing date to the date of death. A subject who has not died will be censored at last known date alive. OS will be followed continuously while subjects are on the treatment and every 3 months via in-person or phone contact after subjects discontinue the study drug.
- DOR is defined as the time from first confirmed response (CR or PR) to the date of the initial objectively documented tumor progression as determined using RECIST 1.1 criteria or death due to any cause, whichever occurs first. For subjects who neither progress nor die, the DOR will be censored on the date of their last evaluable tumor assessment. DOR will only be evaluated in subjects with objective response of CR or PR.
- Objective response rate (ORR) is defined as the number and percentage of subjects with a best overall response (BOR) of confirmed complete response (CR) or partial response (PR).

Best overall response (BOR) is defined as the best response designation, recorded between the date of first dose and the date of the initial objectively documented tumor progression per RECIST v1.1 or the date of subsequent therapy, whichever occurs first. For subjects without documented progression or subsequent therapy, all available response designations will contribute to the BOR determination.

- Progression-free survival (PFS) is defined as the time from first dosing date to the date of the first documented tumor progression, as determined by investigators (per RECIST v1.1), or death due to any cause, whichever occurs first. Subjects who die without a reported prior progression will be considered to have progressed on the date of their death. Subjects who did not progress or die will be censored on the date of their last evaluable tumor assessment. Subjects who did not have any on study tumor assessments and did not die will be censored on the first dosing date.

PRO data will be assessed by measuring change from baseline of the EQ-5D and LCSS scores at each assessment point, and disease-related symptom improvement rate at week 12 measured by LCSS.

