8.2 Populations for Analyses

- All enrolled subjects: all subjects who signed an informed consent form and were registered into the IVRS.
- All treated subjects: all subjects who received any nivolumab. This is the primary population for safety and efficacy analyses. Subpopulation analyses will be conducted by

tumor histology (SQ or NSQ), by subject subgroups (subgroup 1 to 4), and for Cohorts A and B.

- All randomized subjects: all subjects who were randomized to Cohort A or B after completing 1 year of treatment.
- All response evaluable subjects: all treated subjects who have baseline and at least one on-study evaluable tumor measurement.
- [REDACTED]
- [REDACTED]

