8.4.3 Secondary Analyses

The number and percentage of subjects who report high grade (Grade 3-4 and Grade 5) select adverse events will be summarized for all treated subjects. High grade (Grade 3-4 and Grade 5) select adverse events will be tabulated using worst grade per NCI CTCAE v4.0 criteria by system organ class and Medical Dictionary for Regulatory Affairs (MedDRA) preferred term.

Additional descriptive statistics will include median values using the Kaplan-Meier (KM) product-limit method with 95% CI using Brookmeyer and Crowley method of time to onset and time to resolution, and will be presented for all treated subjects, by tumor histology (SQ or NSQ), by subject subgroups, and all randomized subjects for Cohorts A and B. Time to onset is calculated from first dosing date to the event onset date. If a subject never experienced the given AE, the subject will be censored at the last contact date. Time to resolution is calculated from the

AE onset date to AE end date. If an AE is ongoing at the time of analysis, the time to resolution will be censored at the last contact date.

Management of high-grade (CTCAE v4.0 Grade 3-4 and Grade 5) select adverse events will be characterized by measuring percentage of subjects who received immune modulating medication (or hormonal replacement therapy), percentage of subjects who received ≥ 40 mg prednisone equivalents, and total duration of all immune modulating medications given for the event, in all treated subjects who have experienced high-grade (CTCAE v4.0 Grade 3-4 and Grade 5) select adverse events, by tumor histology (SQ or NSQ), and also by subject subgroups, and all randomized subjects in Cohorts A and B.

8.4.4 *Exploratory Analyses*

8.4.4.1 *Safety Analyses:*

All safety data will be summarized and listed for all treated subjects. All on-study AEs, SAEs, treatment-related AEs, and treatment-related SAEs will be summarized using worst grade per NCI CTCAE v4.0 by system organ class and preferred term. On-study lab abnormalities including hematology, chemistry, liver function, thyroid function, and renal function will be summarized using worst grade per NCI CTCAE v4.0 criteria.

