Descriptive statistics of safety (AE and lab data) including incidence, median values using the Kaplan-Meier (KM) product-limit method with 95% CI using Brookmeyer and Crowley method of time to onset and time to resolution, and rate of discontinuation due to event occurrence will be presented for all treated subjects, by tumor histology (SQ or NSQ), by subject subgroups, and all randomized subjects for Cohorts A and B. Time to onset is calculated from first dosing date to the event onset date. If a subject never experienced the given AE, the subject will be censored at the last contact date. Time to resolution is calculated from the AE onset date to AE end date. If an AE is ongoing at the time of analysis, the time to resolution will be censored at the last contact date.

8.4.4.2 *Efficacy Analyses*

[figure not shown]
OS and PFS will be summarized by KM product-limit method for all treated subjects and all response evaluable subjects, respectively. Median values of OS and PFS, along with two-sided 95% CI using Brookmeyer and Crowley method, will be calculated. Survival rates at 6, 12, 18 and 24 months will also be estimated using KM estimates on the OS curve for all treated subjects. Associated two-sided 95% CIs will be calculated using the Greenwood formula. This analysis will be performed for all treated subjects or for all response evaluable subjects for PFS. This analysis will also be performed by tumor histology (SQ or NSQ), by subject subgroups, and all randomized subjects for Cohorts A and B.

The ORR will be summarized by binomial response rates and their corresponding two-sided 95% exact CIs using the Clopper-Pearson method. This analysis will be performed for all response evaluable subjects. This analysis will also be performed by tumor histology (SQ or NSQ), by subject subgroups, and all randomized subjects for Cohorts A and B.

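### OS, PFS and AE onset for Cohorts A and B are timed from first dose instead of the week-52 randomisation, so events from the shared first year enter the trial's only randomised contrast

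*Combined protocol and SAP*

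**What the plan says.** Section 8.3.3 fixes the origin for both time-to-event efficacy endpoints: "OS is defined as the time from first dosing date to the date of death", and "Progression-free survival (PFS) is defined as the time from first dosing date to the date of the first documented tumor progression". For adverse events, Section 8.4.3 states "Time to onset is calculated from first dosing date to the event onset date" and "If a subject never experienced the given AE, the subject will be censored at the last contact date"; Section 8.4.4.1 repeats both rules.

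These definitions are then carried over to the cohorts. Section 8.4.4.2 gives OS landmarks ("Survival rates at 6, 12, 18 and 24 months will also be estimated using KM estimates on the OS curve for all treated subjects") and goes on: "This analysis will also be performed by tumor histology (SQ or NSQ), by subject subgroups, and all randomized subjects for Cohorts A and B". Section 8.4.4.1 does the same for "Descriptive statistics of safety (AE and lab data) including incidence, median values using the Kaplan-Meier (KM) product-limit method", and Section 8.4.3 does so for onset and resolution of high-grade select AEs.

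Section 8.2 defines the randomised population as "all subjects who were randomized to Cohort A or B after completing 1 year of treatment". Section 4.2 puts randomisation at 52 weeks, plus or minus 2 weeks. No readable section gives the cohorts another origin or limits cohort AEs to those arising after assignment.

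**The concern.** Cohort membership cannot affect anything that happened before it was assigned. With a first-dose origin, each cohort summary contains a year in which both groups received the same treatment.

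- **OS.** Everyone randomised was alive at about week 52. The 6- and 12-month cohort rates are therefore fixed by design, and each median carries about 12 months common to both cohorts.
- **PFS.** The event is the first documented progression. Section 4.3.4 allows treatment past RECIST progression. Randomisation requires only that the subject is on treatment (Section 3.1) or still benefiting (Section 4.2), and neither means progression-free. A subject who progressed in year one can be randomised, and that progression is then the cohort PFS event.
- **AEs.** A subject is censored only if the AE never occurred. A first-year AE is therefore the subject's event, and a later one of the same kind and no higher grade adds nothing to incidence or onset.

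At stake is how clearly the trial can describe continuing versus stopping, which Section 1.1.2.1 gives as the purpose of the randomised step.

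**Working it through.** **The plan's own figure.** Section 8.1.1 projects 99 to 322 randomised subjects. From 10/37 = 27.0%, the Wald 95% CI is 12.7% to 41.3%. Then 780 × 0.127 = 99.06 and 780 × 0.413 = 322.14, so the range reproduces. It is the only planning figure for the cohorts; no test, power or effect size is stated.

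**OS landmarks.** Week 50 is 11.50 months and week 54 is 12.42 months after first dose. The cohort landmarks therefore correspond to these times after randomisation:

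| From first dose | From randomisation |
|---|---|
| 6 months | before assignment; OS 100% |
| 12 months | about 0; OS about 100% |
| 18 months | 18 − 12.42 = 5.58 to 18 − 11.50 = 6.50 months |
| 24 months | 24 − 12.42 = 11.58 to 24 − 11.50 = 12.50 months |

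**PFS.** Let f be the share of randomised subjects who progressed before assignment. PFS at 24 months from first dose is about (1 − f) × the progression-free rate 12 months after randomisation. The documents do not give f. Section 1.1.2.1 reports that 9 of 10 subjects still on treatment at one year had durable responses, so at most 1 of 10 had progressed (exact 95% CI 0.25% to 44.5%, which is weak evidence). The planning text does not settle it: the same 10 of 37 are described as on treatment in the Synopsis and as progression-free in Section 8.1.1. With an assumed 60% vs 40% progression-free 12 months after randomisation:

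| f | Displayed rates | Difference |
|---|---|---|
| 0 | 60.0% vs 40.0% | 20 points |
| 5% | 57.0% vs 38.0% | 19 points |
| 10% | 54.0% vs 36.0% | 18 points |

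An f of 5% to 10% is 5 to 10 of 99 subjects, or 16 to 32 of 322.

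**AE incidence.** Let p be the incidence before assignment and q the incidence after it, assumed independent. Incidence from first dose is p + (1 − p) × q, so the displayed difference is (1 − p) × the true later difference.

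The p values for common AEs come from MDX1106-03 (all tumours and doses, whole follow-up) and serve only as proxies. They are 28.1% for treatment-related fatigue, the most frequent single treatment-related AE (Section 1.4.3.2); 140/306 = 46% for any treatment-related select AE (Table 1.1-1); and 230/306 = 75.2% for any treatment-related AE (Section 1.4.3.2). All q values, and the 1% for a rare AE, are assumptions.

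| p | q, A vs B | Displayed | True difference | Displayed difference |
|---|---|---|---|---|
| 1% (rare, high grade) | 3% vs 1% | 3.97% vs 1.99% | 2 points | 1.98 points |
| 28.1% | 40% vs 20% | 56.9% vs 42.5% | 20 points | 14.4 points |
| 46% | 40% vs 20% | 67.6% vs 56.8% | 20 points | 10.8 points |
| 75.2% | 40% vs 20% | 85.1% vs 80.2% | 20 points | 5.0 points |

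**AE onset.** Every randomised subject is followed past assignment, so the Kaplan-Meier curve stands at 1 − p at that point. If p exceeds 50%, both cohort medians lie before assignment and can differ only by chance.

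**The case against.** The strongest reply is that little depends on this. Section 1.1.1 calls the cohort comparison exploratory and descriptive. Only separate medians, rates and intervals are planned, with no hazard ratio or test. Randomisation balances first-year events in expectation, so the first-dose origin dilutes a difference without favouring either cohort. For OS nothing is even diluted, because no randomised subject can have died before assignment. The landmark sentence names the all-treated curve, so its extension to the cohorts depends on how the following sentence is read.

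Prior progression is also probably uncommon. Section 8.1.1 would make it 0 of 10, and retreating Cohort B at progression presupposes mostly unprogressed subjects. The 46% and 75.2% are any-event composites. Of the individual all-causality AEs listed in Section 1.4.3.2, only fatigue (54.9%) exceeds half, so the point about medians applies narrowly. Some Cohort B text is redacted.

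Most of this stands as a limit on size. It does not remove the problem. Balanced earlier events still shrink the displayed contrast, and a descriptive summary still has to describe the period in which the cohorts differ. Cohort onset of high-grade select AEs is also a secondary analysis (Section 8.4.3). The readable endpoint definitions are complete and give only one origin, although Section 3.2 itself counts four years from randomisation within the five-year follow-up.

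Two further points are fair. Worst-grade tables would still register a later, more severe event. DOR, also summarised by cohort, starts at first response, which will often precede week 52.

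**Conclusion.** The concern holds. Followed as written, the plan counts pre-assignment progressions and AEs in the only randomised contrast, and two of the four OS landmarks, if applied to the cohorts, carry no information about continuing versus stopping.

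The size differs by endpoint. The OS difference is almost unchanged. The PFS loss is modest, 1 to 2 points of an assumed 20 if 5% to 10% progressed earlier. Rare high-grade AE differences are essentially unchanged. The main effect is on common, any-grade AEs, where an assumed 20-point difference could show as 14.4 to 5.0 points for the p values used. Those figures rest on assumed post-randomisation rates, independence, and first-year rates borrowed from another study; the true first-year rates in randomised subjects are not in the documents. The primary all-treated analysis is unaffected. This should be corrected, but it does not threaten the main result.

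**What to change.** In Sections 8.3.3, 8.4.3 and 8.4.4, for Cohorts A and B only:

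- Start OS, PFS and AE time to onset at the randomisation date.
- Report OS rates at 6, 12, 18 and 24 months after randomisation.
- Analyse cohort PFS in subjects without RECIST progression before randomisation, and report the number excluded per cohort. The exclusion uses only pre-randomisation facts, so it does not depend on the assigned cohort.
- Tabulate by cohort the AEs with onset on or after randomisation, and show earlier AEs separately.
- State how cohort DOR is to be read, given that response usually precedes assignment.

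Keep the first-dose origin for the all-treated, histology and subgroup analyses.

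The cost is wording plus modest programming: a second time origin, a flag for prior progression and split AE tables. No new data are needed, because the IVRS performs the randomisation. The drawbacks are that cohort medians will look about a year shorter, and that the cohort PFS population will be slightly smaller than the cohort OS population.

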8.4 Analyses

8.4.1 Demographics and Baseline Characteristics

Demographics, baseline disease characteristics and baseline laboratory results will be summarized using descriptive statistics for all treated subjects and all randomized subjects for Cohorts A and B.

8.4.2 Primary Analyses

The number and percentage of subjects who report high grade (Grade 3-4 and Grade 5) treatment related select adverse events will be summarized for all treated subjects. High grade (Grade 3-4 and Grade 5) treatment related select adverse events will be tabulated using worst grade per NCI CTCAE v4.0 criteria by system organ class and Medical Dictionary for Regulatory Affairs (MedDRA) preferred term.

8.4.3 Secondary Analyses

The number and percentage of subjects who report high grade (Grade 3-4 and Grade 5) select adverse events will be summarized for all treated subjects. High grade (Grade 3-4 and Grade 5) select adverse events will be tabulated using worst grade per NCI CTCAE v4.0 criteria by system organ class and Medical Dictionary for Regulatory Affairs (MedDRA) preferred term.

Additional descriptive statistics will include median values using the Kaplan-Meier (KM) product-limit method with 95% CI using Brookmeyer and Crowley method of time to onset and time to resolution, and will be presented for all treated subjects, by tumor histology (SQ or NSQ), by subject subgroups, and all randomized subjects for Cohorts A and B. Time to onset is calculated from first dosing date to the event onset date. If a subject never experienced the given AE, the subject will be censored at the last contact date. Time to resolution is calculated from the

AE onset date to AE end date. If an AE is ongoing at the time of analysis, the time to resolution will be censored at the last contact date.

Management of high-grade (CTCAE v4.0 Grade 3-4 and Grade 5) select adverse events will be characterized by measuring percentage of subjects who received immune modulating medication (or hormonal replacement therapy), percentage of subjects who received ≥ 40 mg prednisone equivalents, and total duration of all immune modulating medications given for the event, in all treated subjects who have experienced high-grade (CTCAE v4.0 Grade 3-4 and Grade 5) select adverse events, by tumor histology (SQ or NSQ), and also by subject subgroups, and all randomized subjects in Cohorts A and B.

8.4.4 *Exploratory Analyses*

8.4.4.1 *Safety Analyses:*

All safety data will be summarized and listed for all treated subjects. All on-study AEs, SAEs, treatment-related AEs, and treatment-related SAEs will be summarized using worst grade per NCI CTCAE v4.0 by system organ class and preferred term. On-study lab abnormalities including hematology, chemistry, liver function, thyroid function, and renal function will be summarized using worst grade per NCI CTCAE v4.0 criteria.

Descriptive statistics of safety (AE and lab data) including incidence, median values using the Kaplan-Meier (KM) product-limit method with 95% CI using Brookmeyer and Crowley method of time to onset and time to resolution, and rate of discontinuation due to event occurrence will be presented for all treated subjects, by tumor histology (SQ or NSQ), by subject subgroups, and all randomized subjects for Cohorts A and B. Time to onset is calculated from first dosing date to the event onset date. If a subject never experienced the given AE, the subject will be censored at the last contact date. Time to resolution is calculated from the AE onset date to AE end date. If an AE is ongoing at the time of analysis, the time to resolution will be censored at the last contact date.

8.4.4.2 *Efficacy Analyses*

[figure not shown]
OS and PFS will be summarized by KM product-limit method for all treated subjects and all response evaluable subjects, respectively. Median values of OS and PFS, along with two-sided 95% CI using Brookmeyer and Crowley method, will be calculated. Survival rates at 6, 12, 18 and 24 months will also be estimated using KM estimates on the OS curve for all treated subjects. Associated two-sided 95% CIs will be calculated using the Greenwood formula. This analysis will be performed for all treated subjects or for all response evaluable subjects for PFS. This analysis will also be performed by tumor histology (SQ or NSQ), by subject subgroups, and all randomized subjects for Cohorts A and B.

The ORR will be summarized by binomial response rates and their corresponding two-sided 95% exact CIs using the Clopper-Pearson method. This analysis will be performed for all response evaluable subjects. This analysis will also be performed by tumor histology (SQ or NSQ), by subject subgroups, and all randomized subjects for Cohorts A and B.

The assessed DOR will be summarized for all response evaluable subjects who achieve confirmed PR or CR using the Kaplan-Meier (KM) product-limit method. Median values of DOR, along with two-sided 95% CI using Brookmeyer and Crowley method, will also be calculated. In addition, the percentage of responders still in response at different time points (3, 6, 12, 18, and 24 months and at end of study) will be presented based on the DOR KM plot. This analysis will be performed for all response evaluable subjects who achieve confirmed PR or CR. This analysis will also be performed by tumor histology (SQ or NSQ), by subject subgroups, and all randomized subjects for Cohorts A and B.

